### Topical products:

The following topical products are authorized on the treated areas:

- Cetaphil® Gentle Skin Cleanser
- Cetaphil® Dermacontrol Moisturizer SPF 30 (once the topical study drug has dried)
- Cetaphil® Moisturizing Lotion (once the topical study drug has dried)

### Systemic treatments:

The following systemic medications are permitted if they are not indicated for the treatment of acne vulgaris:

- The use of non-steroidal anti-inflammatory drugs (NSAIDs) is acceptable for up to 21 days (cumulative) of treatment; however, it should be avoided during the 1-week period prior to the final study assessment (Week 24).
- Topical antibiotics prescribed for localized dermal infections.
- Penicillin G or V.

## 5.4.12.5 Prohibited Medication/Therapy

Medications/therapies listed in Table 4 are prohibited during the study as they may interfere with efficacy and/or safety assessments.

### Table 4: List of Prohibited Medications/Therapies During Study

### **Topical treatments on the face:**

- Corticosteroids, antibiotics, benzoyl peroxide, azelaic acid, alpha hydroxyl acids, salicylic acid, zinc containing treatments, other anti-acne treatments or other acne treatments (e.g., salicylic acid treatments)
- Retinoids
- Cosmetic/aesthetic procedures on the face (e.g., comedo extraction, desquamating or abrasive agents, adhesive pore cleansing strips)
- Wax epilation
- Photodynamic therapy
- Laser therapy, microdermabrasion, deep chemical peel, plastic surgery for acne
- Agents with potential drying effects on the skin: i.e. antibacterial soaps, astringents, other alcohol-containing topical preparations
- Use of tanning booths or lamps, as well as sunless tanning products for the duration

### **Systemic treatments:**

- Initiate use of combined oral contraceptives (estrogens and progesterone), implantable/injectable contraceptives, hormonal contraceptive vaginal rings or change of dose (of existing medication)
- Initiate use of combined oral contraceptives approved as acne treatments (e.g., Ortho Tri-Cyclen®, Yaz®, Diane-35®), or change of dose (of existing medication)
- Corticosteroids (except locally acting corticosteroids such as inhaled or intrathecal), antibiotics (except penicillin G and V)
- Oral retinoids / isotretinoin
- Cyproterone acetate / chlormadinone acetate
- Spironolactone
- Immunomodulators
- Vitamin A supplements exceeding the recommended daily allowance (4000 5000 IU)
- Prescription testosterone therapy (e.g., testosterone cypionate, testosterone enanthate, testosterone pellet, testosterone undecanoate) or on a testosterone booster or prescription testosterone (e.g., DHEA, Omnadren®, Sustanon®, testosterone cypionate, testosterone enanthate, testosterone propionate, testosterone phenylpropionate) or testosterone supplements (e.g., Tribulus)
- Anticoagulants and Methoxyflurate

#### Other:

Any drugs (topical or systemic) or procedures that are used off label for the treatment of acne vulgaris

GALDERMA R&D RD.06.SPR.204245 V00 18AUG2021 Page 50 of 104

If a prohibited therapy becomes necessary for the safety of the subject, the investigator should notify the medical monitor and discuss possible alternatives. If a subject receives a prohibited therapy during the clinical study (e.g., inadvertent short-term use), the investigator should also notify the medical monitor and discuss whether or not it is appropriate for the subject to continue receiving study drugs.

# 5.5 Duration of Subject Participation

The expected duration for each subject's participation in the study is approximately 7 months (24 weeks (6 months) of treatment and up to 28-day period between screening and baseline).

## 5.5.1 Early Termination Visit

When a subject does not complete the clinical study, he/she will be fully assessed, if such assessment is possible. The procedures designated for the Week 24/Early Termination visit should be completed for all subjects discontinuing the study and the appropriate CRF page should be completed.

Refer to Section 5.3.4 for reasons for early study discontinuation.

### 5.5.2 Unscheduled Visit

The subject should be reminded to adhere to the study visit schedule. Unscheduled visits are unplanned and may include examinations for safety or repeat study assessments. Visits occurring outside of the visit window are not considered unscheduled visits.

Assessments to be conducted at the unscheduled visit will depend on the reason for the visit: Any of the procedures/assessments listed in Section 5.1.1.2 Schedule of Assessments may be conducted, as appropriate.

### **6 STUDY ASSESSMENTS**

The protocol specifies the planned efficacy and safety assessments.

Subjects who are wearing a face mask should continue to do so until seated in an exam room, in accordance with your local guidelines. The general sequence of examinations should begin with a wellness assessment, review of dosing calendar/compliance and completion of subject questionnaires prior to performing acne assessments (IGA, lesion counts), local tolerability assessment and imaging (for designated imaging centers).

Any facial observations clearly judged by the investigator to be related to the mask (e.g. erythema or dermatitic effects) will be noted in source records and included in the CRF comments, attributable to the mask (e.g., increased erythema along mask edge, etc). An AE form

GALDERMA R&D RD.06.SPR.204245 V00 18AUG2021 Page 51 of 104

can be submitted at the discretion of the investigator. If mask effects remain detectable at the time of the acne assessments and local tolerability assessments, they should be considered and reported as part of these assessments.

Refer to Section 5.1.1.2– Schedule of Assessments for guidelines to ensure safety of enrolled subjects and continuity of scheduled follow-up visits.

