# 6.3.5 Local Tolerability Assessment

Local tolerability assessment(s) on the face will include erythema, scaling, dryness and burning/stinging. at visits specified in the schedule of assessments (Section 5.1.1.2). Table 9 summarizes the local tolerability assessment. Burning/stinging will be recorded by the investigator after discussion with the subject.

GALDERMA R&D RD.06.SPR.204245 V00 18AUG2021 Page 60 of 104

Local tolerability assessments for the face are reported as a global rating for each tolerability parameter, based on clinical judgment of the investigator.

**Table 9:** Local Tolerability Assessment

Erythema – abnor	Erythema – abnormal redness of the skin						
None	0	No erythema					
Mild	1	Slight pinkness present					
Moderate	2	Definite redness, easily recognized					
Severe	3	Intense redness					
Scaling – abnorm	al sh	edding of the stratum corneum					
None	0	No scaling					
Mild	1	Barely perceptible shedding, noticeable only on light scratching or rubbing					
Moderate	2	Obvious but not profuse shedding					
Severe	re 3 Heavy scale production						
Dryness – brittle a	and/o	or tight sensation					
None	0	No dryness					
Mild	1	Slight but definite roughness					
Moderate	2	Moderate roughness					
Severe	3	Marked roughness					
Stinging/Burning	– pri	icking pain sensation immediately after dosing					
None	0	No stinging/burning					
Mild	1	Slight warm, tingling/stinging sensation; not really bothersome					
Moderate	2	Definite warm, tingling/stinging sensation that is somewhat bothersome					
Severe	3	Hot, tingling/stinging sensation that has caused definite discomfort					

The severity of each sign and symptom should be based after the last topical study drug application before each visit. The Investigator will ask open-ended questions, taking care not to influence the subject's answer, such as "Have you experienced any sensations such as stinging/burning after the last dose of study medication?"

An Adverse Event page must be completed for local tolerability signs and symptoms if the severity of the signs and symptoms assessed with the local tolerability scale is such that:

• The subject permanently discontinues the treatment at his/her request or at the Investigator's request

OR

• The subject requires concomitant treatment, including OTC products or any other medications (other than moisturizer).

GALDERMA R&D RD.06.SPR.204245 V00 18AUG2021 Page 61 of 104

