Any new sign or symptom, which is not included in the scheduled evaluation of tolerability, should be recorded as an Adverse Event, including those of mild intensity.

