### 6.3.6 Adverse Events

Adverse events (AEs) are to be monitored throughout the course of the clinical trial. All AEs are to be reported on the Adverse Event Form with complete information as required. If AEs occur, the main concern will be the safety of the subjects. At the time of the ICF signature, each subject must be provided with the name and phone number of clinical trial center personnel for reporting AEs and medical emergencies.

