# 6.3.6.1.3 Adverse Events of Special Interest

An AESI is a noteworthy treatment-emergent event for the particular study drug that can be appropriate for the Sponsor to monitor closely. It could be serious or non-serious and AESIs could include events that might be potential precursors or prodromal symptoms for more serious medical conditions in susceptible individuals.

The AEs of Special Interest for this protocol are pre-defined as follows:

- Erythema, scaling, dryness, stinging/burning, and other related cutaneous AEs which lead to permanent treatment discontinuation
- Suspicion of allergic contact reaction related to the study drug (see Section 6.3.6.2.4)

GALDERMA R&D RD.06.SPR.204245 V00 18AUG2021 Page 63 of 104

For AESIs, the Investigator is required to complete the AESI Form, within 72 hours of the event, and follow the AESI reporting procedures in Section 6.3.6.1.3 even if the event is considered non-serious according to the usual regulatory criteria.

For suspected sensitizations associated with topical study medication use, follow the rechallenge with assigned topical study drug patch test procedures in Section 6.3.6.2.4 (and subsequent ingredient patch testing, if the rechallenge with assigned topical study drug is positive or equivocal).

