## 6.3.6.2 Reporting Procedures

### 6.3.6.2.1 Procedures for Reporting Adverse Events

The collection of AEs is from the time that a subject sign the ICF to their final visit.

At each post enrollment visit, the Investigator (or sub-Investigator) will question the subject about AEs using an open non-persuasive question to elicit reporting of AEs, for example: "Have you noticed any change in your health since the last visit?" Directed questioning and examination will then be performed, as appropriate.

Any AE occurring during the AE reporting period, whether it is related to the study drug or not, will be recorded immediately in the source document, and described on the Adverse Event Form

GALDERMA R&D RD.06.SPR.204245 V00 18AUG2021 Page 65 of 104

along with the date of onset, severity, relationship to the study drug, and outcome, without omitting any requested and known information. Additional information may be requested under certain circumstances. Adverse Events assessed as related to the treatment will be monitored until they are completely or satisfactorily resolved. Other AEs will be monitored until the last visit if they are not resolved or satisfactorily resolved.

The Investigator will obtain and maintain in the subject's files all pertinent medical records, information and medical judgment from colleagues who assisted in the treatment and follow-up of the subject. If necessary, the Investigator will contact the subject's personal physician or hospital staff to obtain further details.

For SAEs (see Section 6.3.6.2.2), AESIs (see Section 6.3.6.2.3), and pregnancies (see Section 6.3.6.2.5), refer to the sections listed for further reporting requirements.

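### Protocol Section 6 makes the AE form optional for facial findings judged to be mask-related, which conflicts with the AE recording rules, mainly for untreated dermatitis

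*Protocol*

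**What the plan says.** Protocol Section 6 sets a rule for mask effects: "Any facial observations clearly judged by the investigator to be related to the mask (e.g. erythema or dermatitic effects) will be noted in source records". The CRF comments are to carry them too. It adds that an AE form "can be submitted at the discretion of the investigator". For mask effects still visible when acne and local tolerability are assessed, it says "they should be considered and reported as part of these assessments".

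The adverse event sections do not mention masks:

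- Section 6.3.6: "All AEs are to be reported on the Adverse Event Form with complete information as required".
- Section 6.3.6.1.1 defines an AE to include any new sign, or a clinically significant worsening of an existing one, irrespective of relation to the product.
- Section 6.3.6.2.1: "Any AE occurring during the AE reporting period, whether it is related to the study drug or not, will be recorded immediately in the source" (the sentence goes on to require a description on the AE form as well).
- Section 6.3.5, closing paragraph: "Any new sign or symptom, which is not included in the scheduled evaluation of tolerability, should be recorded as an Adverse Event, including those of" (the sentence ends by naming mild signs).
- Section 6.3.5, for the four scored signs (erythema, scaling, dryness, stinging/burning): "An Adverse Event page must be completed for local tolerability signs and symptoms if the severity of the signs and symptoms assessed" on the scale leads to permanent discontinuation or to treatment beyond a moisturizer. Section 5.4.8 sets the same threshold.
- Section 6.3.6.1.3 lists as AESIs "Erythema, scaling, dryness, stinging/burning, and other related cutaneous AEs which lead to permanent treatment discontinuation", with a form due within 72 hours.

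Section 4.2.4 names AE incidence and local tolerability as separate safety endpoints. SAP 4.11.2 tabulates coded treatment-emergent AEs, and SAP 4.11.5 tabulates the tolerability scores. The visible SAP text has no mask rule and no analysis of CRF comments.

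**The concern.** Section 6 lets a judgement about cause decide whether an AE form is filed at all. Elsewhere the protocol does this in the other order: the event is recorded, and its relationship to study drug is then assessed under Section 6.3.6.1.7, with confounding factors taken into account. The order matters here because the study cream goes on the same facial skin. The label in Appendix 14.9 lists application site rash, allergic dermatitis and erythema among its adverse reactions.

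A site that follows Section 6 as written can breach Sections 6.3.5, 6.3.6 and 6.3.6.2.1, and two investigators can record the same dermatitis differently without either departing from Section 6. An event that exists only as a CRF comment does not enter the coded AE tables. The SAP safeguard that counts a missing relationship as related cannot operate either, because there is no AE record to apply it to.

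**Working it through.** The plan states no figure on this point, so the check is a comparison of texts. For each kind of mask-attributed finding, I compare what Section 6 allows with what the AE sections require, and ask whether any other rule leads to an AE form.

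1. **Scored sign below the threshold** (for example erythema that needs no treatment and does not stop the cream). Section 6: form optional. Sections 6.3.5 and 5.4.8: form not required, reading this specific threshold as governing the four signs ahead of the general definition. There is no conflict. If still visible at the visit, the sign is scored under local tolerability and tabulated under SAP 4.11.5.

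2. **Scored sign above the threshold** (permanent discontinuation, or treatment beyond a moisturizer). Section 6: form optional. Section 6.3.5: form mandatory, and the discontinuation cases are AESIs under Section 6.3.6.1.3. The texts conflict. Other rules also lead to a form: Section 5.4.8 classes these cases as AEs, Section 5.4.12.1 generally requires an AE form for a new therapy, and Table 1 in Section 5.3.4 requires one when the study is stopped for an AE.

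3. **Sign outside the scale that is treated, leads to study discontinuation, or is a suspected allergic contact reaction.** Section 6: form optional. Sections 6.3.5, 6.3.6 and 6.3.6.2.1: form required. The texts conflict, but Section 5.4.12.1, Table 1 or the allergic-reaction procedure in Section 6.3.6.2.4 gives another route to a form.

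4. **Sign outside the scale, untreated, with the cream continued.** Table 9 has no item for dermatitis. Any redness or scaling that forms part of it may be scored, but the dermatitis itself is not. Section 6: form optional. Section 6.3.5 (closing paragraph), Section 6.3.6, Section 6.3.6.1.1 and Section 6.3.6.2.1: form required, even if mild and whatever the cause. The texts conflict and no other rule forces a form.

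Case 4 is therefore where Section 6 can actually remove an event from AE incidence. Cases 2 and 3 are conflicts of wording with other safeguards behind them. Case 1 is no conflict.

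For scale, Protocol Section 7.2 plans 60 randomized subjects per arm. One subject whose only AE goes unrecorded changes that arm's AE incidence by 1/60 = 1.67%, or about 1.7 percentage points. The number of such subjects cannot be derived, because the documents give no share of findings attributed to masks.

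**The case against.** The strongest reply is that Section 6 does not discard these findings. They go to source records and CRF comments, and what is still visible is scored under a named safety endpoint. The section's own example, redness along the edge of a mask, would normally fall below the Section 6.3.5 threshold and need no AE form anyway. Treated, discontinuing and allergic cases have other routes to a form, and nothing in Section 6 says that it overrides the mandatory rule in Section 6.3.5. The judgement must also be a clear one, so it is wrong to call it a guess. All of this stands, and it confines the point essentially to case 4. It does not answer case 4.

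A reader might infer that facial irritation in general drops out of AE incidence, and take the label's facial erythema rates as the pool at risk: 30.6 + 28.4 + 6.2 = 65.2% on active against 21 + 6.8 + 0.8 = 28.6% on vehicle. The documents do not support that. Those are tolerability scores, which the label says were collected separately, and erythema below the threshold is not a mandatory AE in this trial.

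A reader might also infer that the active-vehicle difference in cutaneous AEs is materially understated, starting from the label's application site irritation of 7.5% against 0.3%. Those trials covered face and trunk, and a mask cannot explain trunk irritation. Any share assigned to masks would be invented, and investigators are blinded. That losses would fall mainly on the active arm is conjecture.

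**Conclusion.** The point holds in a narrow form. Section 6 contradicts Sections 6.3.5, 6.3.6, 6.3.6.1.1 and 6.3.6.2.1 on whether an AE form is required for mask-attributed dermatitis and other signs outside the tolerability scale. It also contradicts Section 6.3.5 for scored signs that meet the AE threshold. The practical gap is untreated dermatitis with the cream continued, which may be recorded only as a CRF comment and so be missing from the SAP 4.11.2 tables.

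The size is unknown: about 1.7 points of AE incidence per unrecorded subject in an arm of 60, for an unknown number of subjects. This rests on sites following Section 6 literally and on CRF comments not being coded or tabulated, which is how the visible SAP reads. A missed 72-hour AESI report is possible only if a site lets the general mask sentence prevail over the specific rules in Sections 5.4.8, 6.3.5 and 6.3.6.1.3; the documents do not direct that. The efficacy analyses are untouched.

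**What to change.** Reconcile Section 6 with Sections 6.3.5, 6.3.6, 6.3.6.1.1, 6.3.6.1.3 and 6.3.6.2.1 by replacing the discretion sentence with wording such as: *Findings attributed to a face mask follow the same AE and AESI recording rules as any other finding. The suspected mask cause is entered on the AE form together with the relationship to study drug.* Keep the CRF comment as an addition, and keep the instruction to score visible mask effects.

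This applies the existing thresholds and sets no new one. The events then reach the SAP 4.11.2 tables, and those with a suspected mask cause can be listed separately. The cost is one protocol sentence, a few more AE forms, and possibly slightly higher AE rates in both arms.

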# **6.1** Efficacy Assessments

Efficacy measurements should be conducted by the investigators (or trained designees) or by subjects (for subject-reported assessments) according to Section 5.1.1.2 - Schedule of Assessments.

Evaluators must complete standardized training prior to performing the following assessments: Overall Disease Severity Hyperpigmentation,

Refer to Section 8.1 –

Personnel Training for further details on site personnel training. Acne severity grading (IGA) and lesion counts will be performed separately. The acne severity assessments will be performed before the lesion counting.

[figure not shown]
### PIH

Investigator performed activities:

• Overall Disease Severity hyperpigmentation scores (9-point scale) from 0 (Clear) to 8 (Severe) at Screening, Baseline, Week 12, 16, 20 and 24 or early termination visits

CCI			

GALDERMA R&D RD.06.SPR.204245 V00 18AUG2021 Page 52 of 104

7.0

[figure not shown]
GALDERMA R&D RD.06.SPR.204245 V00 18AUG2021 Page 53 of 104

[figure not shown]
# **6.1.1** Overall Disease Severity Scale

[figure not shown]
**Table 5:** Overall Disease Severity Hyperpigmentation

[figure not shown]
Grading Scale	Grading Scale of Outcome Measures						
Grade	Overall Disease Severity						
0	Normal						
1	Present, but < mild						
2	Mild (slightly noticeable)						
3	Between mild and moderate						
4	Moderate (noticeable)						
5	Between moderate and marked						
6	Marked (distinctive)						
7	Between marked and severe						
8	Severe (very distinctive)						

(Grimes, 2006)

[figure not shown]

# 6.3.4 Safety Assessments

Safety assessments include the recording of adverse events and local tolerability scores.

# 6.3.5 Local Tolerability Assessment

Local tolerability assessment(s) on the face will include erythema, scaling, dryness and burning/stinging. at visits specified in the schedule of assessments (Section 5.1.1.2). Table 9 summarizes the local tolerability assessment. Burning/stinging will be recorded by the investigator after discussion with the subject.

GALDERMA R&D RD.06.SPR.204245 V00 18AUG2021 Page 60 of 104

Local tolerability assessments for the face are reported as a global rating for each tolerability parameter, based on clinical judgment of the investigator.

**Table 9:** Local Tolerability Assessment

Erythema – abnor	Erythema – abnormal redness of the skin						
None	0	No erythema					
Mild	1	Slight pinkness present					
Moderate	2	Definite redness, easily recognized					
Severe	3	Intense redness					
Scaling – abnorm	al sh	edding of the stratum corneum					
None	0	No scaling					
Mild	1	Barely perceptible shedding, noticeable only on light scratching or rubbing					
Moderate	2	Obvious but not profuse shedding					
Severe	re 3 Heavy scale production						
Dryness – brittle a	and/o	or tight sensation					
None	0	No dryness					
Mild	1	Slight but definite roughness					
Moderate	2	Moderate roughness					
Severe	3	Marked roughness					
Stinging/Burning	– pri	icking pain sensation immediately after dosing					
None	0	No stinging/burning					
Mild	1	Slight warm, tingling/stinging sensation; not really bothersome					
Moderate	2	Definite warm, tingling/stinging sensation that is somewhat bothersome					
Severe	3	Hot, tingling/stinging sensation that has caused definite discomfort					

The severity of each sign and symptom should be based after the last topical study drug application before each visit. The Investigator will ask open-ended questions, taking care not to influence the subject's answer, such as "Have you experienced any sensations such as stinging/burning after the last dose of study medication?"

An Adverse Event page must be completed for local tolerability signs and symptoms if the severity of the signs and symptoms assessed with the local tolerability scale is such that:

• The subject permanently discontinues the treatment at his/her request or at the Investigator's request

OR

• The subject requires concomitant treatment, including OTC products or any other medications (other than moisturizer).

GALDERMA R&D RD.06.SPR.204245 V00 18AUG2021 Page 61 of 104

Any new sign or symptom, which is not included in the scheduled evaluation of tolerability, should be recorded as an Adverse Event, including those of mild intensity.

